8. STUDY DESIGN

This is an observational retrospective and prospective longitudinal cohort study of several types of fragile patients (see details below). All ages and comorbidities will be included. All the cohorts will be mixed, including patients with and without past or new diagnosis of SARS-CoV2 infection (COVID-19 positive and COVID-19 negative groups) during the study period.

Study will start soon after the approval by the Ethics Committee and will end in June 2023. For the baseline characteristics and past COVID-19 diagnosis, data will be recorded from February 2020. For the prospective part, patients will be recruited until June 2022. Minimum follow-up duration will be of: i) 12 months from the first vaccination dose for fragile patients who will receive anti-COVID-19 vaccination; ii) 18 months from diagnosis of SARS-CoV-2 infection for COVID-19 positive group, allowing a partial follow-up for participants whose SARS-COV-2 infection occur after January 2022; and iii) up to the end of recruitment for the other fragile patients (see Figure 1).

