7. OBJECTIVES

The primary objective of the ORCHESTRA fragile cohorts is to provide an extensive and harmonized collection of epidemiological and clinical data, and biological samples, to assess several features of COVID-19 in each cohort of fragile patients. These include:

- To assess the prevalence of SARS-CoV2 infection and COVID-19 disease in fragile patients;
- To describe the clinical spectrum of COVID-19 disease in different types of fragile patients;
- To analyze epidemiological, clinical and biological predictors of SARS-CoV-2 infection and prognosis in several types of fragile patients;
- To investigate the therapeutic management of COVID-19 and /or of the underlying condition and its impact on the outcome in fragile patients;

- To describe safety and efficacy of COVID-19 vaccination in selected cohorts of fragile patients;
- To describe the relationship between risk perception and adherence to preventive measures over time, including vaccine acceptance;
- To analyze the impact of COVID-19 pandemic on the use of health care services;
- To analyze the socio-economic determinants of infection and disease severity, and the socio-economic impact of the pandemic on cohort specific socio-economic indicators;
- To investigate the psychological consequences of lockdown in fragile patients.
- Identify human genetic markers and epigenetic characteristics in frail patients during post-vaccination monitoring and in the onset of breakthrough infections as well as to analyse the gut microbiome in such patients

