9.8. PENTA Foundation ONLUS – Italy

9.8.1 Italian cohorts

PENTA will participate with the following Italian children cohorts: a large cohort of children followed by primary care paediatricians involved in the “Pedianet” network (COVID-19 and non-COVID-19 subjects) and children attending the clinic for follow-up visits after intra-family COVID-19 infection. Pedianet is an organised network of more than 400 family paediatricians in Italy aimed to collect anonymous data from the electronic system they use in their daily activities to be used for clinical and epidemiological research.

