9.8.3 EPICO cohort

EPICO is a Spanish cohort of currently 1035 children attended in hospitals with COVID-19 with respiratory symptoms or suspected COVID-19 with infection by SARS-CoV-2 confirmed by PCR or serology, from March 2020.

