9.8.4 Bahia cohort

The Instituto Gonçalo Moniz- Fiocruz- Bahia, partnered with the Maternidade de Referência [name] de Magalhães Neto (Maternidade RPJMMN), will also participate in the

ORCHESTRA project with a pregnancy surveillance study that involves pregnant women admitted to Maternidade RPJMMN with suspected COVID-19. The study population will be composed of women with confirmed COVID-19 as well as those with COVID-19-compatible symptoms who test negative for SARS-CoV-2 (control group).

At present, Maternidade RPJMMN has recorded over 300 pregnancies with confirmed or suspected COVID-19 since March 2020.

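### Section 8 calls every cohort mixed by infection status, but EPICO is described as confirmed infections only and two others are selected on suspicion or household infection; including them in prevalence or infection-predictor analyses would select on the outcome

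*Protocol*

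**What the plan says.** Section 8 makes a statement about design without exception: "All the cohorts will be mixed, including patients with and without past or new diagnosis of SARS-CoV2 infection".

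Section 7 lists, among the components of the primary objective, "To assess the prevalence of SARS-CoV2 infection and COVID-19 disease in fragile patients" and "To analyze epidemiological, clinical and biological predictors of SARS-CoV-2 infection and prognosis in several types of fragile patients". The stated aim is "to assess several features of COVID-19 in each cohort of fragile patients".

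Three cohort descriptions in Section 9.8 bear on this:

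- **EPICO (9.8.3):** "EPICO is a Spanish cohort of currently 1035 children attended in hospitals with COVID-19 with respiratory symptoms or suspected COVID-19", and the sentence goes on to say that infection was confirmed by PCR or serology. No uninfected group is mentioned.
- **Bahia (9.8.4, also described in 9.8.2):** the surveillance study "involves pregnant women admitted to Maternidade RPJMMN with suspected COVID-19". It comprises confirmed cases and a control group of symptomatic women who test negative. Over 300 pregnancies had been recorded.
- **Italian clinic cohort (9.8.1):** "children attending the clinic for follow-up visits after intra-family COVID-19 infection". The infection status of the children themselves is not given.

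Most other sites in Section 9 say that they recruit both COVID-19 and non-COVID-19 subjects. Section 13 plans multivariate regression for risk factors and does not limit it to particular cohorts.

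**The concern.** Prevalence and predictors of infection can be estimated only where entry to the cohort does not depend on infection. Section 8 tells the analyst that every cohort has both groups, and so implies that every cohort can serve these two objectives. For EPICO that is untrue as the cohort is described. For Bahia and the intra-family clinic the presence of uninfected subjects may be real, but entry is still tied to suspicion or to household exposure.

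At stake are the first listed component of the primary objective and the infection half of the third. A case-only cohort added to a prevalence estimate pushes it upward. In a model for infection, any trait that is commoner in that cohort than elsewhere, such as childhood, country or hospital attendance, would look like a risk factor even if it has no effect.

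**Working it through.** The protocol gives no expected prevalence and no sample-size calculation, so it has no figure of its own to reproduce. The check sets the texts side by side and then illustrates the size.

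**1. Does each cohort fit Section 8?**

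| Cohort | Entry as described | Uninfected subjects? | Fits Section 8? |
|---|---|---|---|
| EPICO (9.8.3) | Hospital-attended, infection confirmed | None described | No |
| Bahia (9.8.2, 9.8.4) | Admitted with suspected COVID-19 | Yes, test-negative controls | Yes, but selected on suspicion |
| Intra-family clinic (9.8.1) | Follow-up after infection in the family | Not stated | Cannot be judged; selected on exposure |

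The EPICO sentence is awkward. Whether laboratory confirmation applies to all the children or only to the suspected cases, everyone described is a COVID-19 case.

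**2. Within EPICO alone.** All described members are infected, so prevalence is 100% by the entry rule. With no uninfected comparison group, no predictor of infection can be estimated.

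**3. Illustration if EPICO is pooled.**

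Inputs from the documents: E = 1035 (Section 9.8.3) and N = 19784 (Section 9). Assumptions: all 1035 children are counted in N, and the prevalence p in the other cohorts takes the values shown.

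EPICO share: 1035 / 19784 = 5.2%.

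Pooled prevalence = (E + p × (N − E)) / N, with N − E = 18749:

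- p = 5%: (1035 + 937.45) / 19784 = 10.0%
- p = 10%: (1035 + 1874.9) / 19784 = 14.7%
- p = 20%: (1035 + 3749.8) / 19784 = 24.2%

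The ratios to p are 1.99, 1.47 and 1.21, so the distortion shrinks as the underlying prevalence rises.

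**4. Bahia adds little.** Take 300 women, of whom an assumed 30% to 70% are positive, with p = 10%:

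- 30% positive: (1035 + 90 + 0.10 × 18449) / 19784 = 15.0%
- 70% positive: (1035 + 210 + 0.10 × 18449) / 19784 = 15.6%

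No size is given for the intra-family cohort, so its effect cannot be calculated.

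**5. Among children only.** With an assumed m other children at p = 10%, the share is (1035 + 0.10 × m) / (m + 1035):

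- m = 3000: 1335 / 4035 = 33%
- m = 10000: 2035 / 11035 = 18%

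**6. A factor with no true effect.** Assume that it occurs in 10% of subjects elsewhere and that p = 10%. Uninfected subjects come only from the other cohorts: 18749 × 0.9 × 0.1 = 1687.41 with the factor and 18749 × 0.9 × 0.9 = 15186.69 without.

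- 20% in EPICO: infected with the factor 207 + 187.49 = 394.49; without 828 + 1687.41 = 2515.41. Crude odds ratio = (394.49 × 15186.69) / (2515.41 × 1687.41) = 1.41.
- 50% in EPICO: infected with the factor 517.5 + 187.49 = 704.99; without 517.5 + 1687.41 = 2204.91. Crude odds ratio = (704.99 × 15186.69) / (2204.91 × 1687.41) = 2.88.

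Both should be 1.

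**The case against.** The best defence has four parts.

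- **No pooled analysis is stated.** Section 7 speaks of assessing features cohort by cohort. Section 6 does refer to the fragile cohort as a whole as well as each subgroup, but that is rationale and not an analysis specification. Which cohorts enter which model is commonly left to the statistical analysis plan, which is not at hand. This stands: the protocol cannot be said to plan a biased estimate. It does not rescue Section 8, because a separate EPICO estimate is 100% by its entry rule.
- **Bahia is mixed.** Its control group tests negative, so it agrees with Section 8. A test-negative comparison within it is a recognised way to study predictors, as is an analysis conditional on household exposure in the intra-family cohort. This stands, and the remedy should allow for both.
- **The EPICO text describes an existing source cohort**, whereas Section 8 says how study cohorts will be made up. This has some force, but nothing in the protocol says that uninfected children will be added to EPICO.
- **Source size is not enrolled size.** Section 11 asks that patients already diagnosed can be followed to at least 12 months. The stated source sizes 3000 + 300 + 1035 + 1600 + 8534 = 14469 exceed the 10300 that Section 9 counts as registered and on active follow-up. So the 5.2% share is an assumption.

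A reader might infer that several cohorts contain no uninfected patients and that the planned prevalence is inflated. The documents support neither: only EPICO clearly lacks uninfected subjects, and the bias depends on an inclusion that the protocol neither states nor rules out.

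**Conclusion.** The point holds in a limited form. Section 8's statement is wrong for EPICO as Section 9.8.3 describes it. For Bahia and the intra-family clinic, being mixed by status, where that applies, does not make the positive share a population prevalence.

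Bias arises if these cohorts are used for prevalence or for cross-cohort predictors of infection. Under the stated assumptions, pooling EPICO would roughly double a 5% prevalence and raise 20% by about a fifth. The prevalences elsewhere, the full counting of EPICO in the total, the number of other children and the factor frequencies are all assumptions. The upward direction follows from the entry rule whenever prevalence elsewhere is below 100%.

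Analyses among infected patients, such as clinical spectrum, prognosis and sequelae, are not touched by this argument. The correction should be made because the error bears on the first listed objective and is cheap to remove.

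**What to change.** Amend Section 8 so that it no longer claims that all cohorts are mixed, and name the exceptions: EPICO as case-only, Bahia as suspected cases with test-negative controls, and the intra-family clinic as selected on household exposure, with the children's own infection status stated.

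Add that prevalence and cross-cohort infection-predictor analyses use only cohorts whose entry does not depend on infection status, suspicion or household exposure. Keep EPICO for clinical spectrum, prognosis and sequelae. Allow within-cohort comparisons in Bahia (test-negative) and in the intra-family cohort (conditional on household exposure), labelled as such.

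The cost is a protocol wording change, one cohort flag in the database and a smaller denominator for prevalence. No additional data collection follows from it, beyond making each intra-family child's status explicit.

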9. PATIENT COHORTS

The ORCHESTRA fragile population consists of 29 cohorts of 10 different fragile populations including pregnant women/new-born, children, patients with HIV infection, patients with autoimmune disease, solid organ transplant recipients, patients with oncological and hematological diseases, patients with cystic fibrosis, patients with Parkinson Disease and rheumatological diseases from from 14 countries (5 European and 9 non-European countries), with approximately 19784 subjects. Among these, 10.300 individuals are already registered in local databases and on active follow-up in the respective centers. A description of the cohorts is presented in the following sections.

9.1. University of Bologna (UNIBO) – Italy

UNIBO will participate in the recruitment of the following COVID-19 and non-COVID-19 fragile populations: HIV positive, solid organ transplant recipients (liver, kidney, heart, lung),

hematopoietic stem cell transplant recipients, patients with cancer and autoimmune disease patients.

9.2. Azienda-Ospedaliera Universitaria di Parma (AOU di Parma) – Italy

AOU Parma will participate in the recruitment of COVID-19 and non-COVID-19 solid organ transplant (kidney).

9.3. Servicio Andaluz de Salud (SAS) – Spain

SAS will participate in the recruitment of the following COVID-19 and non-COVID-19 fragile populations: HIV positive subjects, solid organ transplant recipients, oncological and hematological patients, hemodialysis patients and rheumatological patients.

9.4. University of Verona (UNIVR) – Italy

UNIVR will participate in the recruitment of the following COVID-19 and non-COVID-19 fragile populations: HIV positive, solid organ transplant recipients, patients with cystic fibrosis, oncological and hematological patients.

9.5. Regione Veneto (REG VEN)– Italy

The Transplant Centers of Treviso, Vicenza and Padova will participate in the recruitment of COVID-19 and non-COVID-19 solid organ transplant recipients (kidney, liver, heart, lung).

9.6. Catholics Bishops Conference of India, Society for Medical Education (CBCI) – India

CBCI will participate in the recruitment of the following COVID-19 and non-COVID-19 fragile populations: HIV positive subjects and patients with auto-immune and rheumatological disorders.

9.7. Universidad de Buenos Aires (UBA) – Argentina

UBA will participate in the recruitment of COVID-19 and non-COVID-19 HIV positive subjects. The cohort, of approximately 100 patients, will be coordinated by the School of Medicine, involving sub-investigators that are already following HIV patients (some of them who already acquired COVID-19) since the beginning of the pandemic in March. Patients will be prospectively enrolled once the study protocol is approved by the Ethics Committee.

9.8. PENTA Foundation ONLUS – Italy

9.8.1 Italian cohorts

PENTA will participate with the following Italian children cohorts: a large cohort of children followed by primary care paediatricians involved in the “Pedianet” network (COVID-19 and non-COVID-19 subjects) and children attending the clinic for follow-up visits after intra-family COVID-19 infection. Pedianet is an organised network of more than 400 family paediatricians in Italy aimed to collect anonymous data from the electronic system they use in their daily activities to be used for clinical and epidemiological research.

9.8.2 EPPICC cohort

European Pregnancy and Paediatric Infections Cohort Collaboration (EPPICC) is a multi-country cohort of children and adolescents living with HIV across Europe and attending routine HIV care. The initial purpose of the cohort was to address key research questions related to long term outcomes of HIV infection and treatment in the paediatric population. The sample size is ~10,000 children/adolescents EVER in follow up included in the database, of which approximately 3000 were in active follow up during 2020.

Pregnant women cohort coordinated by Instituto Gonçalo Moniz- Fiocruz- Bahia, hospital partner: Maternidade de Referência [name] de Magalhães Neto (Maternidade RPJ). In April 2020, a pregnancy surveillance study that involves pregnant women admitted to Maternidade RPJ with suspected COVID-19 was started, with the aim to increase understanding of the risks and impact of COVID-19 during pregnancy and birth outcomes. The study population will be composed of women with confirmed COVID-19 as well as those with COVID-19-compatible symptoms who test negative for SARS-CoV-2 (control group). At present, Maternidade RPJ has recorded over 300 pregnancies with confirmed or suspected COVID-19 since March 2020

9.8.3 EPICO cohort

EPICO is a Spanish cohort of currently 1035 children attended in hospitals with COVID-19 with respiratory symptoms or suspected COVID-19 with infection by SARS-CoV-2 confirmed by PCR or serology, from March 2020.

9.8.4 Bahia cohort

The Instituto Gonçalo Moniz- Fiocruz- Bahia, partnered with the Maternidade de Referência [name] de Magalhães Neto (Maternidade RPJMMN), will also participate in the

ORCHESTRA project with a pregnancy surveillance study that involves pregnant women admitted to Maternidade RPJMMN with suspected COVID-19. The study population will be composed of women with confirmed COVID-19 as well as those with COVID-19-compatible symptoms who test negative for SARS-CoV-2 (control group).

At present, Maternidade RPJMMN has recorded over 300 pregnancies with confirmed or suspected COVID-19 since March 2020.

9.9. University College Dublin (UCD) – Ireland

The All Ireland Infectious Diseases (AIID) Cohort study was initially established at a single hospital site (Mater Misericordiae University Hospital) in 2013. It has since expanded to five hospital sites across Ireland. The aim of the cohort is to create a data-rich prospective dataset derived from patients who present with suspected Infectious Diseases focusing on HIV and Hepatitis and now includes COVID-19. UCD will participate in this protocol recruiting HIV positive subjects including COVID-19 and non-COVID-19 patients.

9.10. Luxembourg Institute of Health (LIH) – Luxembourg

LIH will participate in the recruitment of COVID-19 and non-COVID-19 subjects with Parkinson disease (PD). The Luxembourg Parkinson's Study is a nation-wide and comprehensive clinical, molecular and device-based cohort comprising more than 1,600 participants from Luxembourg and the Greater Region. The cohort includes patients with typical PD and atypical parkinsonism, irrespective of their disease stage, age, comorbidities, or linguistic background (followed-up yearly) and matching control subjects (followed-up every 4 years).

9.11. Translational Health Science and Technology Institute (THSTI) – India

THSTI will participate in the recruitment of a large cohort of COVID-19 and non-COVID-19 pregnant women participating in the GARBH-Ini (interdisciplinary Group for Advanced Research on Birth outcomes - DBT India Initiative) program. GARBH-Ini Cohort was initiated in May 2015 at the Civil hospital in Gurugram (GCH), Haryana, India. Women are enrolled within 20 weeks of gestation and are followed until delivery and once at postpartum. The enrolled women are followed up at 4-5 time-points across 3 trimesters of pregnancy to document extensive clinical & epidemiological information, varied maternal and neonatal biospecimens and for serial ultrasonographic examination. Accounting for a cohort design to detect epidemiological risk factors & nested case-control design for identifying biomarkers, an a priori sample size of 8000 was estimated. More than 8534 pregnant mothers have been

enrolled till February 10, 2020 since May 2015 with documentation of 7260 pregnancy outcomes.

9.12. ZIKAlliance (ORCHESTRA partners: UMCG & UKHD)

ZIKAlliance is a multi-country network coordinated by the ORCHESTRA Partners Academisch Ziekenhuis Groningen (UMCG), Netherlands, and Universitätsklinikum Heidelberg (UKHD), Germany. The initial purpose of this cohort was the evaluation of risks of congenital malformations and other adverse pregnancy outcomes after Zika virus infection in pregnant women and their children. Further, ZIKAlliance has integrated the investigation of SARS-CoV-2 infection and COVID-19 disease into the on-going Zika pregnant women cohort study. ZIKAlliance will participate in this Project with a SARS-CoV-2 substudy including the cohorts of pregnant women and their newborns from Venezuela, Colombia, Ecuador and Peru. Mother and children are followed from birth up to 2 years of age.

9.13. Centre de Recherches Medicales de Lambaréné (CERMEL) – Gabon

CERMEL will participate in the recruitment of children including COVID-19 and non-COVID-19 subjects.

10. INCLUSION AND EXCLUSION CRITERIA

Inclusion criteria are:

[figure not shown]
- Any age
- Person (or attorney or deputy who has been authorized to make the decision for patients who lack capacity) consent to participate, or appropriate local waiver of consent.

The only exclusion criteria will be the lack of consent to participate to the study.

11. STUDY PROCEDURES

In Figure 1, a study work flow is shown.

Figure 1: study work flow

All included patients will be evaluated during the scheduled visits for the underlying condition. During such visits, the following actions are required:

- Distribution of a questionnaire to capture the impact of COVID-19 pandemic on the socio-economic indicators, on the access to health care services, and to investigate risk perception and behavior towards preventing infection and COVID-19 disease, including vaccine acceptance. This questionnaire should be administered at two different time-points with an interval of at least 6 months to capture changes in behavior over the study period (Annex 1a or Annex 1b in case of children cohorts).

- Distribution of psychological scale questionnaires to investigate the impact of lockdown measures on mental health (Annex 2).
- Screening for past and/or current COVID-19 disease by medical interview, serology determination and nasopharyngeal swab or saliva specimens' collection.
- Collection, processing and storage of plasma for cytokine and chemokine analysis.
- Collection, processing and storage of serum for the subsequent sero-neutralization and type I IFNs autoantibodies detection.
- Collection, processing and storage of PBMCs for the subsequent anti-COVID-19 cellular immunity analysis.
- Collection, processing and storage of whole blood for genetic and epigenetic analysis.
- Collection, processing and storage of nasopharyngeal samples for SARS-CoV-2 detection and variant identification if clinically relevant.
- Collection, processing and storage of stool samples for metagenomic sequencing.
- In immunocompromised fragile cohorts, laboratory tests to assess the baseline “net state of immunosuppression” including whole blood count, lymphocyte differentiation, immunoglobulin levels, and complement (C3) levels should be done at the baseline (first clinical evaluation).

For patients with a past and/or new diagnosis of SARS-CoV2 infection/COVID-19 disease a pre-established long-term follow-up including multiple diagnostic levels in order to adapt to all the participating cohorts is requested. A detailed overview of the schedule of the study visits and the clinical parameters to be recorded is shown in **Table 1**. Patients who have already had COVID, and new patients being diagnosed with COVID, who can be followed up to at least 12 months, and for whom data can be collected according to **Table 1** should be included. In specific fragile cohorts, such as children cohorts, virtual assessments are allowed.

For patients who have been or will be vaccinated against COVID-19 during the study period, a pre-established monitoring of safety and efficacy in terms of immunological response will be performed. A detailed overview of the schedule of the clinical and laboratory parameters to be recorded is shown in **Table 2**. Patients who have already been vaccinated, or will be vaccinated, who can be followed for 12 months, and for whom data can be collected according to Table 2 should be included. The monitoring should start from the days of first and second dose administration when possible (i.e. vaccination administered in the same center where the patient is followed for the fragile condition), alternatively patients will be monitored at 3±1, 6±2 and 12±3 months after the first vaccination dose.

- Vaccination safety will be assessed by a dedicated questionnaire (Annex 3) distributed to patients at baseline or during the first monitoring visit.

- Vaccination efficacy will be established analyzing the immune response at the predefined time-points. The humoral immune response to vaccination will be assessed by a serological assay able to detect anti-Spike and anti-Nucleocapsid antibodies as well as seroneutralization assays in sera samples. The latter will be useful to exclude possible natural infection at the baseline (1st/2nd dose, or first post-vaccination monitoring visit). The cytokine and cell-mediated immune response to vaccination will be assessed in a subgroup of patients by centralizing samples to a referral laboratory, according to local ethic rules and budget. The number of SARS-CoV-2 paucisymptomatic or symptomatic infection despite vaccination will be also assessed by SARS-CoV-2 detection in respiratory/saliva sample.

During the post-vaccination monitoring and in the onset of a breakthrough infection after one or two doses of the anti-SARS-CoV-2 vaccine, several analyses (genomic, transcriptomic, cytokine, viral, genetic and epigenetic) will be performed in a local or centralised laboratory according to the type of testing realized (see Table 3):

- PBMCs for characterisation of T-cell immune response will be sent to University of Antwerpen
- Plasma for cytokinome analysis will be sent to University of Antwerpen
- Serum for autoantibodies against type I IFNs detection will be sent to INSERM or University of Antwerpen
- Whole blood samples for epigenetic and genetic analysis will be sent to UNIBO, INSERM and HMGU. In-depth human genetic analysis will be conducted using WGS or whole exome sequencing (WES) followed by functional analyses of the most promising variants.
- Nasal swabs for characterization of viral markers and respiratory microbiome dynamics will be sent to University of Antwerpen or INSERM.
- Stool samples for intestinal microbiome profiling will be sent to University of Bologna.

Detailed instructions on sample collection, processing, storage, shipment and destination sites are provided in the WP6 protocol (WP6, D 6.1) attached as Annex 4.

Table 3 – Overview of samples collection, processing, storage and destination sites.

| Sample | Aliquot | Sample type | Volume | Storage solution | Storage temp. (°C) | Shipping temp. (°C) | Task | Comment | Partner |
|-----------------------------|----------------|---|---|---|---|---------------------|--|--|--------------------|
| PBMC | 1 or 2 samples | PBMC | | 0.5 ml FBS/DMSO 20% | -70°C or below or liquid nitrogen | Dry ice | Characterisation of T-cell immune response | | UANTWERPEN |
| Blood | 1 | EDTA plasma, but heparin plasma or serum can also be used, if EDTA plasma is absolutely unavailable | 350 µL | EDTA plasma has to be processed according to the protocol provided before freezing (preferably at -80°C directly) | Short term at -20 °C, long term at -70°C or below | Dry ice | Cytokine analysis | Please process and freeze within 2 hours. | UANTWERPEN |
| | 2 | Serum/plasma | 200 µL | NA | -20°C, long term at -70°C or below | Dry ice | Auto-antibodies against type I IFNs | If available | INSERM |
| | 3 | Serum | 100 µL | NA | -20°C, long term at -70 ° or below | Dry ice | Antibodies detection | | INSERM; UANTWERPEN |
| Whole blood | 1 | Extracted DNA or whole blood | 4 µg if DNA, 2 ml if whole blood | NA | -20°C/ -80°C | Dry ice | NGS of COVID-19 cohorts | DNA could be extracted locally or at HMGU. | INSERM/UNIBO |
| | 2 | DNA or whole blood | 750 ng in 45 µL if extracted DNA; otherwise 1 aliquot | TE buffer or water if extracted DNA | -20°C | Dry ice | Illumina EPIC DNA methylation | DNA could be extracted locally or at HMGU. | HMGU |
| NP swab | 1 | NP swab | 400 µL | TRIzol; RNA later; DNA/RNA shield | -70°C or below | Dry ice | Characterisation of viral markers Respiratory microbiome dynamics | | UANTWERPEN- INSERM |
| Stool sample or rectal swab | 1 | Stool (faecal swab if stool is unavailable) | 1-2 g | RNA later if possible, otherwise frozen. | +4°C (up to 24 h) long term at -70°C or below | Dry ice | Intestinal microbiome profiling | | UNIBO |

